**3. To test the effect of repeated t-PBM sessions on impaired decision making, in subjects with impulsivity due to BD**

*Hypothesis:* repeated t-PBM sessions on the R-dlPFC will significantly improve decision making – increase in net gain at the Iowa gambling task, decrease in Barratt Impulsiveness Scale (BIS) score at day 5 and follow-up visit relative to baseline, decrease in BRIEF-A score at day 5 and follow-up visit relative to baseline, and a decrease in I-7 Impulsiveness and Venturesomeness Questionnaire score at day 5 and follow-up visit relative to baseline.

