### **3. General Description of Study Design**

This is a single-blind study to test the neuropsychological and clinical effects of t-PBM with NIR in BD. For our primary aim of examining the effect of tPBM on CBF, the study is additionally sham-controlled. Twenty patients with a diagnosis of bipolar disorder, not currently in a depressive, manic, or mixed state episode, will undergo one sham and one NIR- t-PBM session on day 1 (within MRI scanner), and one daily NIR- t-PBM session from day 2 to 5. On day 5, the NIR t-PBM session will also occur in the MRI scanner. The fMRI scan will measure BOLD changes during sham t-PBM (day 1) and during NIR t-PBM (day 1 & 5), on R-dlPFC.

Impulsivity will be assessed by the BIS at pre-screen (for inclusion criteria), baseline, treatment day 5, and the follow-up visit; and by the gambling tasks at baseline, after the first NIR t-PBM (day 1), after the fifth NIR t-PBM (day 5), and at the follow-up visit. Other aspects of impulsivity and executive functioning will be assessed by the I-7 and BRIEF-A at baseline, day 5, and the follow-up visit. The MOODS-SR-Last Week will be administered at baseline, day 5, and the follow-up visit to assess change in mood, particularly hypomanic symptoms. At screening, subjects will complete the MOODS-SR Lifetime.

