### *Columbia Suicide Severity Rating Scale (C-SSRS)*

An instrument endorsed by the FDA for clinical trials. This instrument systematically tracks suicidal ideation and behavior (e.g., suicide attempts, wish to die, thoughts of suicide, plan, and intent).

*Concomitant Medications and Therapies Form*

This form records all ongoing medications, as well as other therapies, and will be completed at every study visit, including the screening visit, as a safety-monitoring tool.

*Iowa Gambling Task*

In this computerized task, participants play a game of chance in which they can win or lose fake money. Participants are presented with four cards and are asked to choose one. Their choice results in a gain or loss. Participants are given feedback on each choice. This task is designed to measure impulsivity.

*Delgado Gambling Task (IGT)*

In this computerized task, participants play a game of chance in which they can win or lose fake money. Participants are given a target number. They are then presented with a sequence of cards. Before each card is presented, participants are asked to guess whether the number on the next card will be higher or lower than the target number. They are then given feedback on their choice. This task is designed to measure reward-processing.

*I-7: Impulsiveness and Venturesomeness Questionnaire*

The I-7 is a self-report scale of 54 items and three subscales. Of the 54 items, 19 measure Impulsiveness, 16 measure Venturesomeness, and 19 measure Empathy. Answers are marked as “Yes” or “No.”

*Mini International Neuropsychiatric Interview (M.I.N.I)*

The M.I.N.I. is a short structured diagnostic interview, developed jointly by psychiatrists and clinicians in the United States and Europe, for DSM and ICD psychiatric disorders. With an administration time of approximately 15 minutes, it is designed to meet the need for a short but accurate structured psychiatric interview for clinical trials. According to researchers at the National Institute of Mental Health's (NIMH) Division of Clinical and Treatment Research, the M.I.N.I. is a fully validated and more time-efficient alternative to the Structured Clinical Interview for DSM Disorders (SCID). For the purposes of this study, we will only use modules related to mood, psychosis, and substance abuse.

*MOODS-SR – Last Week & Lifetime*

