## 9. Statistical Analysis

Preprocessing of MRI and fMRI data will be performed with the FreeSurfer software package, scripted in Bash. Slice-time correction, motion-correction, and co-registration of functional BOLD scans, Time of Repetition (TR), and participant will then be performed. BOLD signals will then be smoothed to a full-width half maximum (FWHM) of 3mm and z-scored at every voxel.

t-PBM related increase of BOLD percent signal change (PSC) averaged across all ROI voxels will be assessed during the first scanning session where the participant receives both sham and NIR over the R-dlPFC. PSC of t-PBM related increase in BOLD both during and after stimulation will be the dependent variable with the independent variable being the condition of t-PBM during the first session (sham vs. NIR).

BOLD signal will again be assessed during the 5th NIR session as a PSC across all ROI voxels in comparison with the BOLD PSC from the first NIR session to observe any BOLD changes after 5 NIR treatment sessions. The dependent variable will be the BOLD signal and the independent variable will be the timepoint: day 1 vs. after 5 sessions (day 5).

For both gambling tasks, the gambling task net gain score will be analyzed for changes from baseline to after treatment on day 1, baseline vs day 5, and baseline vs follow up. The BIS, BRIEF-A, and I-7 will be analyzed for changes from baseline to day 5 and follow up. Here, the dependent variable will be the gambling tasks' net gain scores, BIS, BRIEF-A, and I-7 total score. The independent variable is the timepoint baseline vs. day 5 (for the gambling tasks) and follow up. The MOOD-SR will also be analyzed for a decrease in impulsivity at each timepoint of baseline vs. day 5 and follow up. A General Mixed Models Regression will be used with time as a fixed effect and subject as a random effect.

Secondary analyses will also be performed for the BIS, BRIEF-A, I-7, MOOD-SR, SAFTEE, and TSRQ. Each scale and their respective subscales will be analyzed for specific changes at

each timepoint to better understand the effect t-PBM NIR has on the symptoms and presentation of BD. These additional analyses will also be helpful in assessing the initial safety profile of t-PBM in this psychiatric population.

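### The I-7 total score used for Aim 3 is not defined; as the scale is described, 19 of its 54 items (35%) measure empathy, which no aim concerns

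*Combined protocol and SAP*

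**What the plan says.** Section 2 states Aim 3 as "To test the effect of repeated t-PBM sessions on impaired decision making, in subjects with impulsivity due to BD". Its hypothesis lists four measures: Iowa gambling task net gain, BIS, BRIEF-A and I-7. For the last it predicts a "decrease in I-7 Impulsiveness and Venturesomeness Questionnaire score at day 5 and follow-up visit relative to baseline".

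Section 3 gives the purpose of the instrument: "Other aspects of impulsivity and executive functioning will be assessed by the I-7 and BRIEF-A".

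The I-7 entry under Assessments in Section 6 reads "The I-7 is a self-report scale of 54 items and three subscales", and continues "Of the 54 items, 19 measure Impulsiveness, 16 measure Venturesomeness, and 19 measure Empathy". Answers are yes or no. The entry gives no scoring rule.

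Section 9 sets the dependent variables as the gambling tasks' "net gain scores, BIS, BRIEF-A, and I-7 total score". It then adds a further layer: "Secondary analyses will also be performed for the BIS, BRIEF-A, I-7, MOOD-SR, SAFTEE, and TSRQ", and "Each scale and their respective subscales will be analyzed for specific changes at" each timepoint. The power statement in Section 9 covers Aim 1 only.

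**The concern.** The I-7 is in the study to measure impulsivity, and a lower score is meant to show better decision making. As the scale is described, though, it has as many Empathy items as Impulsiveness items. If the total adds up all 54, the Aim 3 variable mixes the intended construct with one on which the study has no hypothesis. Three things could follow:

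- Falling Empathy would push the total in the hypothesised direction, although nothing in the protocol treats less empathy as a benefit.
- Rising Empathy would offset a real fall in Impulsiveness.
- Unchanged Empathy would generally add variance without signal.

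A change in the I-7 total could then not be read as a change in impulsivity without the subscale results. Those are labelled secondary, and the plan does not say how to read a disagreement between them and the total.

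**Working it through.** **1. Item counts (documented, Section 6).** 19 + 16 + 19 = 54, which reproduces the stated length. Empathy is 19/54 = 35.2%, Impulsiveness 19/54 = 35.2% and Venturesomeness 16/54 = 29.6%. Without Empathy, 35/54 = 64.8% of the items remain.

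**2. What the text settles.** Empathy is named only in the I-7 entry. None of the four aims mentions it. Section 9 says total score without defining it, and no section removes or reverses any items.

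**3. How much it could matter (illustration only).** The documents give no subscale SDs, correlations or effects, so all of the following are assumptions:

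- The SD of change is proportional to item count, so the weights are w = (1, 16/19, 1) = (1, 0.842, 1) for Impulsiveness, Venturesomeness and Empathy.
- A common correlation ρ between subscale changes runs from -0.2 to 0.4.
- A subscale that changes falls by d = 0.5.
- The test is a paired t with n = 20 and two-sided alpha 0.05. The plan's own model is a mixed regression over timepoints, so this is a stand-in.

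For a sum of subscales, d = Σ(wᵢdᵢ) / √(Σwᵢ² + 2ρΣwᵢwⱼ).

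Example at ρ = 0 with only Impulsiveness falling:

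- 54 items: 0.5/√(1 + 0.709 + 1) = 0.5/√2.709 = 0.304, power 25%.
- 35 items: 0.5/√1.709 = 0.382, power 37%.
- 19 items: d = 0.5, power 56%.

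Power over ρ = -0.2, 0, 0.2, 0.4:

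| What falls by 0.5 | 54-item total | 35 items | 19 items |
|---|---|---|---|
| Impulsiveness only | 38, 25, 19, 16% | 44, 37, 32, 28% | 56% |
| Impulsiveness and Venturesomeness | 86, 66, 52, 43% | 92, 85, 78, 72% | 56% |
| Empathy only (hypothetical) | 38, 25, 19, 16% | 5% | 5% |

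**4. When an Empathy-free score would lose power.**

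- *35 items against the total, Empathy unchanged.* The signal is the same, so the total wins only if adding Empathy lowers the variance: 1 + 2r(1 + 16/19) < 0, where r is the correlation of Empathy change with each of the other two subscales. This gives r < -1/3.684 = -0.27.
- *35 items against the total, Empathy also falling.* The total can then have more power. If all three fall by 0.5 at ρ = 0, the total has d = 0.5 × 2.842/√2.709 = 0.863 and power 95.5%, against 84.8% for 35 items.
- *19 items against the total, Impulsiveness and Venturesomeness both falling.* The total wins if 1.842² > 2.709 + 5.368ρ, that is ρ < (3.393 - 2.709)/5.368 = 0.13.

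**The case against.** **The total may already leave Empathy out.** Aim 3 calls the measure by a name that mentions only Impulsiveness and Venturesomeness. That may be no more than the questionnaire's title, but it leaves room for a two-subscale score. A reader might infer that the Empathy items are shown to be in the Aim 3 variable. The documents do not support that: the total is undefined, and summing all 54 items is only the plainer reading. The objection stands as a limit on the claim, but the request survives it, because Section 9 has to name the score on either reading.

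**The subscales are analysed anyway.** This is largely right. An Empathy-driven change in the total would be visible. What remains is that the total is the named Aim 3 variable, and that nothing says which result governs if total and subscale differ.

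**Nothing turns on this score.** A reader might infer that a fall in Empathy could make Aim 3 succeed. The documents set no success rule: they list four measures without saying how many must improve. Aim 3 is also unpowered, and sham control is confined to the blood-flow aim. So the consequence is for interpretation, not for a decision.

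**The remedy is not neutral.** Also right. Venturesomeness, like Empathy, appears in no aim except through the questionnaire's name, so the documents do not settle whether it belongs in the score. The 19-item choice can have less power than the total, and so can the 35-item choice if Empathy also falls. In the latter case the extra power comes from an off-target construct, so it is no reason to keep the total.

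**Conclusion.** The concern holds in a limited form. The plan uses an undefined I-7 total for Aim 3. On the plain reading, 35% of its items measure a construct with no hypothesis, and the protocol neither excludes nor reverse-scores them. The documented size is that item share. The power figures only illustrate the mechanism under assumed SDs, correlations and effects, and should not be quoted as properties of this trial. In particular, nothing in the documents suggests that Empathy alone would fall.

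One of four Aim 3 measures is affected, and the planned subscale analyses already limit the harm. Severity: minor.

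**What to change.** In Section 9, before results are seen, replace the I-7 total with one pre-specified Empathy-free score: either the 19-item Impulsiveness subscale or Impulsiveness plus Venturesomeness (35 items). State how it is scored, and report Empathy descriptively.

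The cost is one or two sentences. No new data are needed, because subscale analyses are already planned. The sponsor has to choose between the two scores, and the trade-off is real. On the illustrative assumptions, the shorter score does better if only Impulsiveness falls (56% against 44 to 28%). The longer one does better if both fall equally (92 to 72% against 56%). In that second pattern, with Empathy unchanged, the shorter score also has less power than the present total when the common correlation is below about 0.13.

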### **4. Subject Selection**

We intend on enrolling 30 subjects diagnosed with bipolar disorder, with the goal of randomizing 20 subjects.

Inclusion criteria for this study include: 1) adults between the ages of 18 and 65, 2) diagnosis of bipolar disorder assessed with M.I.N.I. diagnostic interview, 3) currently experiencing symptoms of impulsivity as per BIS total cut-off score equal or greater than 70, 4) if of child-bearing potential must agree to use adequate contraception (e.g. oral contraceptives, intrauterine device, double barrier methods, or total abstinence from intercourse), and 5) vision corrected to normal with contacts/vision does not require glasses or other visual aids.

Exclusion criteria for this study include: 1) currently in depressive, manic, or mixed episode; 2) currently psychotic; 3) judged to be at serious and imminent suicidal risk (C-SSRS $\geq$ 4); 4) currently in alcohol or substance use disorder (meeting criteria in the past 3 months as assessed with M.I.N.I. diagnostic interview); 5) unstable medical conditions; 6) inability to consent or to complete study procedures; 7) failure to meet standard MRI safety requirements (e.g. claustrophobia, non-removable piercings, implanted medical devices, other non-removable metals) as determined by the MRI Safety Checklist; 8) changes in medications or use of augmentative devices and other interventions in the 2 weeks prior to the study; 9) participation in other clinical research trials that may influence primary outcomes or adherence to the proposed study, as assessed by the PI and the Co-Is; and 10) current pregnancy.

Source of subjects will include outpatient clinics at MGH and McLean, the Translational and Clinical Research Center, and Registries/Patient Databases such as the RPDR and Patient Gateway Announcements and or Invitations. We will recruit primarily through referrals from physicians, flyers, online advertisements, and platforms such as Partners Rally and ResearchMatch. We will respond to all individuals who express interest in the study, whether it is from an online recruitment source or through a referral from outpatient clinics at MGH. Clinical research coordinators will primarily handle recruitment and outreach, though some tasks may fall to other members of study staff, like interns. Physicians may send referrals directly to [name], who will forward the information to a CRC to make contact.

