## Assessments

### *Adverse Events Form*

The Adverse Events Form captures any adverse event (serious or otherwise) that the subject experiences while participating in the study. Events may occur during or outside of study procedures.

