This 161-item self-report scale assesses manic-depressive symptoms. Participants are asked to answer “Yes” or “No” to each question. Subdomains measure Moods, Energy, Cognition, and Rhythmicity. Time frame is either lifetime or the last week, depending on scale used.

*MRI Safety Checklist*

This form identifies risk factors that may make MRI participation unsafe.

*New Immigrant Survey-Skin Color Scale (NIS-SCS)*

The NIS-SCS is an 11-point scale, ranging from zero to 10, with zero representing albinism, or the total absence of color, and 10 representing the darkest possible skin. The ten shades of skin color corresponding to the points 1 to 10 on the Massey and Martin Skin Color Scale are depicted in a chart, with each point represented by a hand, of identical form, but differing in color. The respondent never sees the chart. We gather this data for use as a potential covariate in analyses as skin color can affect absorption of NIR.

*Patient Health Questionnaire (PHQ-9)*

This nine-item self-report measure assesses the presence and severity of depressive symptoms over the past 14 days. This scale will be administered as part of the pre-screening phase.

*Perceived Blinding Questionnaire (PBQ)*

The PBQ is a self-report questionnaire to determine the degree to which the participant believes they are receiving active treatment or sham.

*Prior Treatment Log*

This form captures information regarding prior treatments for bipolar disorder or other mental health concerns.

*Systematic Assessment for Treatment Emergent Events (SAFTEE)*

The SAFTEE is a commonly used instrument originally developed by NIMH and adapted into a self-report instrument. The version of the scale that we plan to use is the same used by the multi-center, NIMH-sponsored CO-MED trial, and it examines in a systematic fashion all possible treatment-emergent side effects and probes specific adverse symptoms, including suicidal thoughts and behaviors, and self-injurious behavior.

*t-PBM Self-Report Questionnaire (TSRQ)*

An open-ended questionnaire focusing on potential inconveniences and discomforts from the t-PBM treatment.

*Young Mania Rating Scale (YMRS)*

This 11-item clinician-rated scale is used to assess the presence and severity of manic symptoms.

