*Risks of tPBM:* The study laser device emits light with a longer wavelength than the human eye can see. The staff will be provided training on basic safety procedures relative to the use of the device. The staff administering the t-PBM will be careful not to operate the laser unless it is in direct contact with the subject’s skin. Protective eyewear is required since the device is a laser. Failure of laser device, resulting in the cessation of investigative therapy can cause no adverse event to our knowledge. Delivery of the infrared laser energy to an inappropriate site, such as directly over the open eye, would pose risk to the subject, such as blindness. Based on previous observations with similar laser devices, application of the laser may result in mild thermal sensation of warmth during use. The temperature of the skin is however kept well below the level for thermal damage. Based on human clinical trial experience to date and on sale of t-PBM devices for their intended use (e.g. Omnilux New-U), each adverse event listed below has been

reported by less than 0.1% of all subjects and users: erythema, pain, discomfort, warmth, headache, or other reactions at the application site. In our research experience, t-PBM devices could produce insomnia, irritability, and fleeting illusions. The modality of administration for t-PBM with the study laser device is analogous to the protocols used in our feasibility studies. The dose of light delivered by the study device is analogous to our feasibility studies and to published studies on t-PBM. No serious adverse events occurred during our feasibility trials.

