*Power and Detectable Effects:* The study is powered (G\*Power 80%) to answer Aim #1 for a moderate effect size (Cohen's  $d \geq 0.5$ ), based on a Wilcoxon signed-rank test (matched pairs; one-tailed; alpha=0.05). Dmochowski et al. demonstrated a BOLD increase as high as 31% (dlPFC) within a single t-PBM session and in healthy subjects (pre- and post-t-PBM; Cohen's  $d=0.374$ ). In our current design, we will compare NIR versus sham (also within a t-PBM session) in 20 subjects with impulsivity due to BD, therefore we anticipate a larger effect size.

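### Section 9 draws on SAFTEE and TSRQ score changes for the safety profile, names no summary statistic for them and plans no adverse-event tabulation; it should prespecify per-participant incidence with exact intervals

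*Combined protocol and SAP*

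**What the plan says.** Section 9 (Statistical Analysis) places the two tolerability instruments in one list with the impulsivity and mood scales: "Secondary analyses will also be performed for the BIS, BRIEF-A, I-7, MOOD-SR, SAFTEE, and TSRQ". The next sentence gives the method, "Each scale and their respective subscales will be analyzed for specific changes at" each timepoint, and the paragraph closes with its safety purpose: "These additional analyses will also be helpful in assessing the initial safety profile of t-PBM in this psychiatric population". No statistic is named for SAFTEE or TSRQ. The only model in the section is a mixed model with time fixed and subject random, stated at the end of the preceding paragraph.

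The Assessments part of Section 6 describes the instruments. Of the SAFTEE it says "it examines in a systematic fashion all possible treatment-emergent side effects" and that it asks about specific symptoms. The TSRQ is an open-ended questionnaire on inconvenience and discomfort from the treatment. The Adverse Events Form "captures any adverse event (serious or otherwise) that the subject experiences while participating in the study"; its fields are not described. Section 9 does not mention that form.

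Section 7 (Risks of tPBM) names the effects to look for. It lists erythema, pain, discomfort, warmth, headache and other reactions at the application site, and adds: "In our research experience, t-PBM devices could produce insomnia, irritability, and fleeting illusions".

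**The concern.** The effects named in Section 7 are events that happen to individuals. The natural questions are how many participants had each one and how high the true rate could be. A change in a scale or subscale score answers neither. It pools unrelated symptoms, and one participant's improvement can offset another's new complaint. At this sample size a harm confined to two or three people barely moves a mean.

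If the safety statement were drawn mainly from such changes, it could contain no rate and no upper limit for insomnia, irritability or any other named effect. The protocol's own tables of earlier experience with this device (Section 6, tPBM Administration) already use the more informative layout: participants, incidences, severity, relatedness and resolution. No section plans that layout for this trial.

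**Working it through.** **Inputs.** The sample size is 20, from Section 4 ("with the goal of randomizing 20 subjects"). The plan gives no safety figure to reproduce. Its only design figure concerns the imaging aim ("The study is powered (G\*Power 80%) to answer Aim #1") and plays no part here. The documents give no SAFTEE scoring or SD, so the shifts below are assumptions, shown over a range.

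**1. Which data cover which visits (Section 6).**
- SAFTEE: baseline, Treatment 5 and follow-up only.
- TSRQ: after each of the five treatments, with no score, subscale or baseline described. The analysis in Section 9 therefore cannot be run on it as described.
- Adverse events: baseline, Treatments 2 to 5, the check-in call and follow-up. The Treatment 1 text does not list them.
- CAST-IRR, an irritability measure: baseline and all five treatments. It is also absent from Section 9.

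**2. A single item, with nobody else changing.** Suppose k of n participants worsen by S points and the rest stay at zero. The mean change is kS/n and the variance is kS²(n − k)/[n(n − 1)]. The one-sample t is then √[k(n − 1)/(n − k)], and S cancels.
- k = 2: t = √(2 × 19/18) = 1.45, p = 0.163.
- k = 3: t = √(3 × 19/17) = 1.83, p = 0.083. With S = 2 the mean change is 0.30.
- Three worse and three better by the same amount: mean 0, p = 1.0.

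This is an illustration. The plan names scales and subscales, not items.

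**3. A scale or subscale with noise.** Change scores for 20 people were simulated as normal with SD 1, and k of them were shifted by S SDs. A paired t-test stood in for the time contrast (two-sided 0.05, 40,000 runs). The table gives the mean change in SDs and the chance of a significant worsening.

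| S | 2 of 20 affected | 3 of 20 affected |
|---|---|---|
| 1 | 0.10; 5.4% | 0.15; 7.5% |
| 2 | 0.20; 7.6% | 0.30; 12.7% |
| 3 | 0.30; 8.8% | 0.45; 16.0% |
| 4 | 0.40; 8.6% | 0.60; 17.8% |

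Larger shifts help little, because a few extreme values also inflate the SD. If all 20 participants also improve by 0.2 SD, the chances fall to 0.7% to 1.4% (two affected) and 1.1% to 4.2% (three affected).

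**4. The same data as counts, exact (Clopper-Pearson) 95% intervals.**
- 0/20: upper limit 1 − 0.025^(1/20) = 16.8%.
- 2/20 = 10%: 1.2% to 31.7%.
- 3/20 = 15%: 3.2% to 37.9%.

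The chance of seeing at least one affected participant is 1 − (1 − p)^20: 64% at a true rate of 5%, 88% at 10% and 96% at 15%.

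**The case against.** The strongest reply is that averaging is not written into the plan. Section 9 names no statistic for SAFTEE, the mixed-model sentence belongs to the previous paragraph, and a symptom-by-symptom reading of specific changes is open. That stands: mean change is an inference from the only model in the section. If another summary is meant, it is unstated, and the same fix supplies it.

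Second, Section 9 calls these analyses helpful towards a safety profile and does not say that a non-significant change will count as safety. That also stands. A reader might infer that the trial will report harms as no change, but this predicts the write-up and nothing in the documents commits the authors to it.

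Third, events are handled individually under Section 10: weekly staff review, review by the principal investigator, and annual reports to an independent monitor. The TSRQ also asks about discomfort after every session. A harm in two or three people would therefore probably be noticed. But monitoring does not produce a reported rate. Section 10 also keeps expected events out of IRB reports unless they are judged unexpected, although another sentence there has the principal investigator report adverse events to the IRB. The earlier studies' tables mostly code warming, headache and insomnia as expected, so these are the effects that most need a planned table.

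Fourth, severity and relatedness may not be on the Adverse Events Form. Its description lists no fields, and the columns in the earlier tables come from other studies. The fix must therefore be conditional on what is recorded.

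**Conclusion.** The point holds as a gap in the planned safety analysis. Section 9 relies on score changes with no stated summary, one of its two tolerability instruments cannot be scored as described, and no section plans a count of affected participants, an incidence or an interval.

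If SAFTEE is summarised by mean change, a harm in 2 or 3 of 20 participants would probably show no significant worsening. Detection is roughly 5% to 18% for shifts of 1 to 4 SD with no other change, and lower if the group improves. These figures rest on assumed shifts, normal noise and a t-test. The exact intervals need only the 20 participants.

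Two stronger readings are not supported. The documents do not show that harms would go unseen, because monitoring is separate from Section 9. Nor do they list worsening mood as an effect of t-PBM: Section 7 links it to holding medication unchanged. This should be changed, but it does not affect the imaging aim.

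**What to change.** In Section 9, make per-participant incidence the safety summary:

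- **SAFTEE:** the number of participants with any item new or worse than their own baseline at Treatment 5 or follow-up, and the number for each item.
- **Adverse Events Form and coded TSRQ complaints:** the number of participants with an event starting at or after the first active session. Count each person once per event type, by severity and relatedness where recorded. Use one relatedness scale, since the two earlier tables use 1 to 5 and 0 to 4.
- **Intervals:** exact (Clopper-Pearson) 95% intervals for the effects named in Section 7: insomnia, irritability, fleeting illusions, headache, and warmth, erythema, pain or discomfort at the site.
- **Denominator:** everyone who received at least one active t-PBM session. List events during the day 1 sham separately, because the sham comes before the active session.
- **Score change:** keep SAFTEE change as a descriptive line, and state that a non-significant change is not evidence of safety.

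The cost is wording, one table and a simple coding list for the TSRQ free text, with no new visits or participants. The downside is wide intervals: even no events in 20 people leaves an upper limit of 16.8%, so the safety statement will read less favourably.

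### The stated 80% power at d ≥ 0.5 is not reproduced with 20 pairs: on the ordinary reading it is about 68%, and 80% needs a favourable assumption that the plan does not state

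*Combined protocol and SAP*

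**What the plan says.** The power paragraph of Section 9 makes the claim in these terms: "Power 80%) to answer Aim #1 for a moderate effect size", defined as Cohen's d of at least 0.5, "based on a Wilcoxon signed-rank test (matched pairs; one-tailed; alpha=0.05"). The comparison is to be made "in 20 subjects with impulsivity due to BD". Section 4 gives an enrolment target of 30, "with the goal of randomizing 20 subjects", and Section 3 has twenty patients each receiving one sham and one NIR session on day 1. The number of pairs is therefore 20.

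Earlier in Section 9, the Aim 1 outcome is assessed "during the first scanning session where the participant receives both sham and NIR over the R-dlPFC", so both measurements come from one scanning session.

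The only prior effect size cited is d = 0.374, a pre/post change "within a single t-PBM session and in healthy subjects". From there the plan moves to its own comparison, "in 20 subjects with impulsivity due to BD, therefore we anticipate a larger effect size". It gives no estimate for NIR against sham in bipolar disorder.

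**The concern.** The test, the sidedness, alpha, d and the number of pairs are all given, so the power should be recoverable. With the usual definitions it comes out well below 80%. Two inputs that G*Power's method depends on are missing: the parent distribution of the differences, and whether d is standardised by the SD of the paired differences or by the SD of a single condition.

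If the ordinary reading is right, the type II error at d = 0.5 is about 32% rather than 20%. A null result on Aim 1 would then be taken as stronger evidence against a moderate effect than 20 pairs can supply. The one effect size cited lies below 0.5, and the expectation of a larger one rests on no figure, so nothing else in the paragraph offsets the shortfall.

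**Working it through.** **Inputs** (Section 9, with the number of pairs confirmed in Sections 3 and 4): n = 20 pairs, one-tailed alpha 0.05, Wilcoxon signed-rank test, d = 0.5 (the smallest effect the claim covers), stated power 80%.

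**Method.** G*Power's asymptotic relative efficiency (A.R.E.) approach uses an effective sample size N′ = n × ARE, a noncentral t distribution with N′ − 1 degrees of freedom, and noncentrality d × √N′. Power is the probability of exceeding the one-tailed 5% critical value.

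**Attempt to reproduce 80%, normal parent** (ARE = 3/π = 0.955):
- N′ = 20 × 0.955 = 19.10, so df = 18.10
- noncentrality = 0.5 × √19.10 = 2.185
- power = 67.6%

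**Other parents, d as the standardised paired difference:**

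| Parent | ARE | Power, n = 20, d = 0.5 | Pairs for 80% at d = 0.5 | d for 80% at n = 20 |
|---|---|---|---|---|
| Minimum ARE | 0.864 | 63.5% | 31 | 0.625 |
| Normal | 0.955 | 67.6% | 28 | 0.592 |
| Paired t-test | 1 | 69.5% | 27 | 0.577 |
| Logistic | 1.097 | 73.2% | 24 | 0.549 |
| Laplace | 1.5 | 84.8% | 18 | 0.465 |

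**Check against the exact test.** For n = 20 the one-tailed exact test rejects when the positive-rank sum is at least 150 (exact size 0.0487). Simulated power at d = 0.5 (400,000 replicates) is 67.3% for a normal parent, 71.5% for logistic and 77.9% for Laplace. The approximation is close for the normal parent and optimistic for Laplace. By exact-test simulation (200,000 replicates):
- normal parent: 27 pairs give 78.8% and 28 give 80.8%
- Laplace parent: 21 pairs give 79.2% and 22 give 81.4%

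With a normal parent and n = 20, simulated power is 79.5% at d = 0.59 and 80.7% at d = 0.60.

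**If d is scaled to the single-condition SD.** The paired-difference effect is then dz = 0.5 / √(2(1 − r)), where r is the sham–NIR correlation. The plan gives no value of r, so a range is shown (normal parent, n = 20):
- r = 0.5: dz = 0.500, power 67.6%
- r = 0.6: dz = 0.559, power 76.0%
- r = 0.7: dz = 0.645, power 85.7%

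Solving for dz = 0.592 gives r = 1 − (0.5/0.592)²/2 ≈ 0.643.

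**Thirty pairs.** With n = 30 and a normal parent, power is 83.3%. But 30 is the enrolment target, and the power paragraph itself names 20 subjects.

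**Sensitivity only.** If the cited d = 0.374 is read as a paired-difference effect (the plan does not say how it was scaled), 20 pairs with a normal parent give 47.1% by the A.R.E. method and 46.7% by simulation.

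**The case against.** The best reply is that the paragraph is under-specified rather than wrong. A normal parent and scaling by the SD of differences are no more stated than the alternatives, and choosing a Wilcoxon test is at least compatible with expecting non-normal differences. With a Laplace parent, G*Power's method needs 18 pairs for 80%, so 20 would leave two spare, and nothing in the plan excludes that choice. Sham and NIR are given to the same person in one session, so a correlation near 0.64 is plausible too, and power then sits almost exactly at 80%. On these readings the type II error is not 32%.

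Much of this stands as a limit on the conclusion: 80% is not impossible, and the 68% is conditional on the usual definitions. It does not rescue the statement as written. Either route needs a specific favourable input, and the plan gives neither. The Laplace route also falls about two points short once the exact test is used. A reader given only the stated inputs cannot arrive at 80%.

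It is also fair to say that the remark about a larger effect is an expectation and not part of the arithmetic, since the 80% is tied to d of at least 0.5. That remark is a secondary point, and the conclusion on power does not depend on it.

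**Conclusion.** The concern holds. With 20 pairs, a one-tailed alpha of 0.05, normally distributed differences and d defined on those differences, power at d = 0.5 is about 68%, some 12 points below the stated 80%. The effect detectable with 80% power is about 0.59, and 28 pairs would be needed for 0.5. A figure of 80% or more arises only under a heavy-tailed (Laplace) parent in the approximation, or with single-condition scaling and a correlation of about 0.64 or more; neither assumption is in the plan. All the figures assume that all 20 pairs are analysable. The power paragraph gives no allowance for lost or unusable scans, and any loss lowers power further. The numbers are secure. What remains open is which inputs the sponsor actually used. This should be corrected, but it does not threaten the conduct of the study.

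**What to change.** Keep the sample size and restate the power paragraph along these lines:

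> With 20 analysable pairs, assuming normally distributed paired differences and d defined as the mean difference divided by the SD of the differences, a one-tailed Wilcoxon signed-rank test at alpha 0.05 has 80% power for d of approximately 0.59 or more and about 68% power for d = 0.5. As a sensitivity value only, power is about 47% at d = 0.374.

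If the 80% came from another parent distribution, or from a single-condition SD with an assumed correlation, state that input and justify it instead. For a Laplace parent, also note that the exact test gives about 78%.

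Remove the sentence expecting a larger effect, or support it with an estimate for the NIR-versus-sham contrast.

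The cost is protocol wording only: no extra patients and no change to conduct or analysis. The drawback is that the stated detectable effect becomes less favourable, about 0.59 rather than 0.50.
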